11.3. Serious Adverse Events

11.3.1. Definition of Serious Adverse Events

An SAE is defined as an AE that meets at least 1 of the following serious criteria:

- fatal
- life-threatening (places the patient at immediate risk of death)
- requires in-patient hospitalization or prolongation of existing hospitalization
- results in persistent or significant disability/incapacity
- congenital anomaly/birth defect
- other medically important serious event

An AE would meet the criterion of “requires hospitalization”, if the event necessitated an in-patient admission to a health care facility (eg, overnight stay).

If an investigator considers an event to be clinically important, but it does not meet any of the serious criteria, the event could be classified as an SAE under the criterion of “other medically important serious event”. Examples of such events could include allergic bronchospasm, convulsions, blood dyscrasias, drug-induced liver injury, or events that necessitate an emergency room visit, outpatient surgery, or urgent intervention.

Since the criteria for the CTCAE grading scale differs from the regulatory criteria for SAEs, if AEs correspond to grade 4 “life threatening” CTCAE grading scale criteria (eg, laboratory abnormality reported as grade 4 without manifestation of life threatening status), it will be left to the investigator’s judgment to also report these abnormalities as SAEs. For any AE that applies to this situation, comprehensive documentation of the event’s severity status must be recorded in the patient’s medical record.

11.3.2. Reporting Procedures for Serious Adverse Events

Any AE that meets any criterion for an SAE requires the completion of an SAE Report Form in addition to being recorded on the AE page/screen of the eCRF. All SAEs must be reported to Aadi Drug Safety within 24 hours of the investigator’s knowledge of the event by facsimile, or other appropriate method, using the SAE Report Form, or approved equivalent form. This instruction pertains to initial SAE reports as well as any follow-up reports.

The investigator is required to ensure that the data on these forms is accurate and consistent. This requirement applies to all SAEs (regardless of relationship to IP) that occur during the study (from the time of signing of the informed consent form to 28 days after the last dose of IP), and those made known to the investigator at any time thereafter that are suspected of being related to IP.

The SAE report should provide a detailed description of the SAE and include a concise summary of hospital records and other relevant documents. If a patient died and an autopsy has been performed, copies of the autopsy report and death certificate are to be sent to Aadi Drug Safety as soon as these become available. Any follow-up data will be detailed in a subsequent SAE Report Form, or approved equivalent form, and sent to Aadi Drug Safety.

Where required by local legislation, the investigator is responsible for informing the IRB/EC of the SAE and providing them with all relevant initial and follow-up information about the event. The investigator must keep copies of all SAE information on file including correspondence with Aadi and the IRB/EC.

11.4. Pregnancy and Breast Feeding Reporting

If a pregnancy occurs in a female patient, or female partner of a male patient, while the patient is taking protocol-required therapies report the pregnancy to Aadi as specified below. In addition to reporting any pregnancies occurring during the study, investigators should monitor for pregnancies that occur up to 3 months after the last dose of protocol-required therapies.

The investigator will follow the female patient until completion of the pregnancy, and must notify Aadi Drug Safety immediately about the outcome of the pregnancy (either normal or abnormal outcome) using the Pregnancy Follow-up Report Form, or approved equivalent form. If a lactation case occurs while the female patient is taking protocol-required therapies, report the lactation case to Aadi as specified below. In addition to reporting a lactation case during the study, investigators should monitor for lactation cases that occur up to 1 week after the last dose of protocol-required therapies.

12. WITHDRAWAL FROM TREATMENT, PROCEDURES, AND STUDY

12.1. Discontinuation from Investigational Product

The following events are considered sufficient reasons for discontinuing a patient from the IP:

- AE(s) (that are intolerable)
- Physician decision
- Withdrawal of consent (from treatment only)
- Death
- Lost to follow up
- Protocol violation
- Other (to be specified on the eCRF)

The reason for treatment discontinuation should be recorded in the eCRF and in the source documents.

12.2. Discontinuation from the Study

The following events are considered sufficient reasons for discontinuing a patient from the study:

- Withdrawal of consent
- Death
- Lost to follow up
- Protocol violation
- Other (to be specified on the eCRF)

The reason for study discontinuation should be recorded in the eCRF and in the source documents.

At the time of withdrawal, it should be determined whether the patient is withdrawing from treatment alone, or from treatment and collection of further data (eg, survival). Every effort should be made to collect survival data after patient withdraws from treatment.

Patients have the right to withdraw from the study at any time and for any reason without prejudice to his or her future medical care by the physician or at the institution.

12.3. Investigator or Sponsor Decision to Withdraw or Terminate Patient's Participation Prior to Study Completion

The investigator and/or sponsor can decide to withdraw a patient(s) from IP and/or other protocol-required therapies, protocol procedures, or the study as a whole at any time prior to study completion.

Patients may be eligible for continued treatment with Aadi IP and/or other protocol-required therapies by a separate protocol or as provided for by the local country's regulatory mechanism.

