3.3. End of Study, End of Treatment, End of Treatment Visit, Follow-up Period

End of Study (EOS) is defined as either the date of the last visit of the last patient to complete the study, or the date of receipt of the last data point from the last patient that is required for primary, secondary, and/or exploratory analysis, as pre-specified in the protocol.

End of Treatment (EOT) is defined as the date of the last dose of ABI-009.

End of Treatment Visit is when safety and efficacy assessments and procedures are performed after the last treatment. For patients who complete the 16-week treatment, EOT visit occur at week 17 (± 3 days). For a patient who does not complete the 16-week treatment, EOT Visit must occur within 4 weeks (± 7 days) after the last dose of ABI-009.

Follow-up period is the on-study time period for at least 28 days after the last treatment either in the Dose-finding Safety Part or optional Extension Part, whichever is later. All patients that discontinue study drug and have not withdrawn full consent to participate in the study will continue in the follow-up phase for survival and therapy. Follow-up will continue up to 1 year approximately every 12 weeks (± 3 weeks), or more frequently as needed, until withdrawal of consent, or the study closes, whichever is the earliest. This evaluation may be made by record review and/or telephone contact.

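### Sections 12.2 and 12.3 allow a consenting patient to be removed from the study, against the follow-up rule in 3.3, so end-of-treatment and safety follow-up data may be lost

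*Combined protocol and SAP*

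**What the plan says.** The protocol has two lists. Section 12.1 gives reasons for stopping the investigational product. Section 12.2 gives reasons for leaving the study and opens: "The following events are considered sufficient reasons for discontinuing a patient from the study". Alongside withdrawal of consent, death and loss to follow-up, the second list includes "Protocol violation" and "Other (to be specified on the eCRF". Both also appear in 12.1. Section 12.3 adds that the investigator and/or sponsor may withdraw a patient from drug, from procedures, "or the study as a whole at any time prior to study completion", and gives no criteria.

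Section 3.3 sets a different rule: "All patients that discontinue study drug and have not withdrawn full consent to participate in the study will continue in the follow-up phase". That phase lasts up to a year, "until withdrawal of consent, or the study closes, whichever is the earliest". The synopsis (Length of Study) and Table 2 footnote n end follow-up on the same terms. None of the three names a protocol violation or another reason as an exit.

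The only data safeguard within 12.2 concerns survival: "Every effort should be made to collect survival data after patient withdraws from treatment".

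**The concern.** A protocol violation or another reason already allows drug to be stopped under 12.1. Listing the same two reasons in 12.2 also allows observation to end in a patient who has not asked for that. Section 12.3 goes further, because it requires no reason at all.

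The safety profile over 16 weeks and up to 48 weeks is a primary endpoint (2.2, 10.1), and safety analyses use the treated population (10.1). A removed patient who has been dosed stays in that denominator, and any event after removal that goes unrecorded is counted as no event. The study is open-label and the cohorts are small, so a single discretionary removal carries weight. At stake are the EOT visit, the unexpired part of the 28-day AE period, and the later follow-up.

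**Working it through.** **Comparing the rules.** Take a treated patient who stops drug for a protocol violation and still consents.

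| Duty | Where set | How long it runs | Stated to survive removal under 12.2 or 12.3? |
|---|---|---|---|
| Survival and therapy follow-up | 3.3; synopsis; Table 2 footnote n | Up to 1 year, or to consent withdrawal or study closure | 3.3 keeps the patient in; 12.2 and 12.3 allow the patient out |
| AE and SAE recording | 11.1, 11.3.2 | 28 days after last dose, then related SAEs the investigator learns of | Not stated |
| EOT visit for early stoppers | 3.3, 6.3 | Within 4 weeks (±7 days) of last dose | Not stated |
| All assessments in patients off therapy | 14.3 | Per schedule | Duty is for each patient in the study, so arguably not |
| Survival data | 12.2 | Not stated | Covers survival only, after withdrawal from treatment |

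The first row is a contradiction. The others are silent or limited. The 28-day period is affected too, because 3.3 describes the minimum 28-day follow-up as on-study time.

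**The plan's own figures.** These reproduce by counting: 4 levels × 6 = 24 at most in escalation; 3 + 6 = 9 at least; expansion top-up 10 − 6 = 4 to 10 − 3 = 7. A cohort therefore holds 3, 6 or up to 10 patients, and one patient is 1/3 = 33%, 1/6 = 17% or 1/10 = 10% of it.

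**Effect of removals on an observed proportion.** Let n be the patients treated, x the patients with an observed event, and m the patients removed early with no event recorded before leaving. With complete data, the proportion in those n patients lies between x/n (no removed patient had the event) and (x + m)/n (all did). The documents give no value for m, so these are assumed. For n = 10 and x = 1:

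- m = 1: 1/10 to 2/10, or 10% to 20%
- m = 2: 1/10 to 3/10, or 10% to 30%
- m = 3: 1/10 to 4/10, or 10% to 40%

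With the treated population as denominator, the plan would report 1/10 in each case, which is the lower end.

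**Sampling error is separate.** The exact (Clopper-Pearson) 95% interval is 0.3% to 44.5% for 1/10 and 6.7% to 65.2% for 3/10.

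**Chance of any removal.** If each patient has removal probability q, independently, the chance of at least one in ten is 1 − (1 − q)^10. For assumed q of 5%, 10% and 20% this is 40%, 65% and 89%.

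**The case against.** The strongest reply is that 12.2 is permissive. It lists sufficient reasons; it does not require removal or order collection to stop. AE and SAE recording and the early EOT visit are timed from the last dose, not from study status. The synopsis has all SAEs followed to resolution. Section 14.3 keeps the investigator responsible for assessments in patients off therapy, and 12.2 asks whether a withdrawing patient is leaving treatment alone or further data collection as well. Data recorded before removal stay in the analysis.

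Most of this stands, and it limits the point to data that may be lost. It does not close the gap. The duty in 14.3 is for patients in the study; the question in 12.2 concerns a patient who withdraws, not one whom the investigator or sponsor removes; and no section says that the duties timed from last dose continue after removal.

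A reader might also infer that week-17 efficacy data are lost because of the conflict with 3.3. The documents do not support that. The follow-up rule in 3.3 says patients "will continue in the follow-up phase for survival and therapy" and covers no week-17 measures. Patients who stop early have an EOT visit within 4 weeks of last dose, with right heart catheterization optional and analysed separately (6.3). What is exposed is that visit, or week 17 itself only for a patient removed close to it.

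A reader might further infer that removed patients are the ones most likely to differ. The documents report neither how often patients are removed nor who they are, so this is conjecture.

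**Conclusion.** The point holds as a contradiction with a limited consequence. Sections 12.2 and 12.3 permit removal from the study without withdrawal of consent; 3.3, the synopsis and Table 2 footnote n do not. If a site follows 12.2 or 12.3, the EOT visit, the remainder of the 28-day AE window and the survival and therapy follow-up may be lost.

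The possible direction of error follows from the denominator: with removed patients kept in the treated population, missed events can only lower the reported incidence. This does not require removed patients to be unusual.

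The size is unknown. The 10% to 30% range assumes two early removals in a cohort of ten, one event seen, and none recorded in the two before they left. It bounds the sample proportion in those ten patients and should not be read as a range for the underlying event rate, whose uncertainty is wider.

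This is a data-completeness point in a descriptive study. It does not overturn the design, but it should be corrected because it bears on primary safety data.

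**What to change.** - Remove protocol violation and the open-ended other category from 12.2. Both remain in 12.1 as reasons to stop drug, and 12.1 needs no change.
- Align 12.3 with 3.3, so that withdrawing a patient from drug or procedures does not by itself end data collection. Keep an exception for termination of a site or of the study under 13.5.
- State in 12.2, with a cross-reference in 3.3, that the EOT visit, AE and SAE collection to 28 days after last dose, and the later follow-up all continue, and that the patient stays in the treated population, unless the patient dies, is lost to follow-up or withdraws consent to further data collection.

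The cost is amendment wording. The visits and contacts are already scheduled, and the planned numbers (24 at most and 9 at least in escalation, up to 10 per expanded cohort) do not change.

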13. REGULATORY OBLIGATIONS

13.1. Informed Consent

An initial sample informed consent form is provided for the investigator to prepare the informed consent document to be used at his or her site. Updates to the template are to be communicated formally in writing from Aadi to the investigator. The written informed consent document is to be prepared in the language(s) of the potential patient population.

Before a patient's participation in the clinical study, the investigator is responsible for obtaining written informed consent from the patient after adequate explanation of the aims, methods, anticipated benefits, and potential hazards of the study and before any protocol-specific screening procedures or the IP is administered.

The investigator is also responsible for asking the patient if the patient has a primary care physician and if the patient agrees to have his/her primary care physician informed of the patient's participation in the clinical study. If the patient agrees to such notification, the investigator is to inform the patient's primary care physician of the patient's participation in the clinical study. If the patient does not have a primary care physician and the investigator will be acting in that capacity, the investigator is to document such in the patient's medical record.

The acquisition of informed consent and the patient's agreement or refusal of his/her notification of the primary care physician is to be documented in the patient's medical records, and the informed consent form to be signed and personally dated by the patient or a legally acceptable representative and by the person who conducted the informed consent discussion. The original signed informed consent form is to be retained in accordance with institutional policy, and a copy of the signed consent form is to be provided to the patient or legally acceptable representative.

If a potential patient is illiterate or visually impaired and does not have a legally acceptable representative, the investigator must provide an impartial witness to read the informed consent form to the patient and must allow for questions. Thereafter, both the patient and the witness must sign the informed consent form to attest that informed consent was freely given and understood.

13.2. Institutional Review Board/Independent Ethics Committee

A copy of the protocol, proposed informed consent form, other written patient information, and any proposed advertising material must be submitted to the IRB for written approval. A copy of the written approval of the protocol and informed consent form must be received by Aadi before recruitment of patients into the study and shipment of Aadi IP.

The investigator must submit and, where necessary, obtain approval from the IRB for all subsequent protocol amendments and changes to the informed consent document. The investigator is to notify the IRB of deviations from the protocol or SAEs occurring at the site and other AE reports received from Aadi, in accordance with local procedures.

The investigator is responsible for obtaining annual IRB approval [IRBs only]/renewal [IRBs and IECs] throughout the duration of the study. Copies of the investigator's reports and the IRB continuance of approval must be sent to Aadi.

13.3. Patient Confidentiality

The investigator must ensure that the patient's confidentiality is maintained for documents submitted to Aadi.

- Patients are to be identified by a unique patient identification number.
- Where permitted, date of birth is to be documented and formatted in accordance with local laws and regulations.
- On the CRF demographics page, in addition to the unique patient identification number, include the age at time of enrollment.
- For SAEs reported to Aadi, patients are to be identified by their unique patient identification number, initials (for faxed reports, in accordance with local laws and regulations), and date of birth (in accordance with local laws and regulations).
- Documents that are not submitted to Aadi (eg, signed informed consent forms) are to be kept in confidence by the investigator, except as described below.

In compliance with Federal regulations/ICH GCP Guidelines, it is required that the investigator and institution permit authorized representatives of the company, of the regulatory agency(s), and the IRB direct access to review the patient's original medical records for verification of study-related procedures and data. Direct access includes examining, analyzing, verifying, and reproducing any records and reports that are important to the evaluation of the study. The investigator is obligated to inform and obtain the consent of the patient to permit such individuals to have access to his/her study-related records, including personal information.

13.4. Protocol Amendments

If Aadi amends the protocol, agreement from the investigator must be obtained. The IRB must be informed of all amendments and give approval. The investigator must send a copy of the approval letter from the IRB to Aadi.

13.5. Termination of the Study

Aadi reserves the right to terminate the study at any time. Both Aadi and the investigator reserve the right to terminate the Investigator's participation in the study according to the study contract. The investigator is to notify the IRB in writing of the study's completion or early termination and send a copy of the notification to Aadi.

14. DATA HANDLING AND RECORDKEEPING

14.1. Data/Documents

The investigator must ensure that the records and documents pertaining to the conduct of the study and the distribution of the investigational product are complete, accurate, filed, and retained. Examples of source documents include: hospital records; clinic and office charts; laboratory notes; memoranda; checklists; dispensing records; recorded data from automated instruments; copies or transcriptions certified after verification as being accurate copies; microfiche; x-ray film and reports; and records kept at the pharmacy; and the laboratories, as well as copies of eCRFs or CD-ROM.

14.2. Data Management

Data will be collected via eCRF and entered into the clinical database. These data will be electronically verified through use of programmed edit checks specified by the clinical team. Discrepancies in the data will be brought to the attention of the clinical team, and investigational site personnel, if necessary. Resolutions to these issues will be reflected in the database. An audit trail within the system will track all changes made to the data.

14.3. Investigator Responsibilities for Data Collection

The investigator is responsible for complying with the requirements for all assessments and data collection (including patients not receiving protocol-required therapies) as stipulated in the protocol for each patient in the study. For patients who withdraw prior to completion of all protocol-required visits and are unable or unwilling to continue the Schedule of Assessments ([Table 2](#)), the investigator can search publicly available records (where permitted) to ascertain survival status.

This ensures that the data set(s) produced as an outcome of the study is/are as comprehensive as possible.

14.4. Sample Storage and Destruction

Any blood, biomarker or pharmacokinetic sample collected according to the Schedule of Assessments ([Table 2](#)) can be analyzed for any of the tests outlined in the protocol and for any tests necessary to minimize risks to study patients. This includes testing to ensure analytical methods produce reliable and valid data throughout the course of the study. This can also include, but is not limited to, investigation of unexpected results, incurred sample reanalysis, and analyses for method transfer and comparability.

If informed consent is provided by the patient, Aadi can do additional testing on remaining samples (ie, residual and back-up) to investigate and better understand the disease, the dose response and/or prediction of response to ABI-009, and characterize aspects of the molecule (eg, mechanism of action/target, metabolites). Results from this analysis are to be documented and maintained, but are not necessarily reported as part of this study. Samples can be retained for up to 20 years.

Since the evaluations are not expected to benefit the patient directly or to alter the treatment course, the results of biomarker, biomarker development, or other exploratory studies are not placed in the patient's medical record and are not to be made available to

the patient, members of the family, the personal physician, or other third parties, except as specified in the informed consent.

The patient retains the right to request that the sample material be destroyed by contacting the Investigator. Following the request from the patient, the investigator is to provide the sponsor with the required study and patient number so that any remaining blood or tumor samples and any other components from the cells can be located and destroyed. Samples will be destroyed once all protocol-defined procedures are completed.

The sponsor is the exclusive owner of any data, discoveries, or derivative materials from the sample materials and is responsible for the destruction of the sample(s) at the request of the patient through the Investigator, at the end of the storage period, or as appropriate (eg, the scientific rationale for experimentation with a certain sample type no longer justifies keeping the sample). If a commercial product is developed from this research project, the sponsor owns the commercial product. The patient has no commercial rights to such product and has no commercial rights to the data.

